HIV continues to be a global concern, but the focus on HIV treatment and research have shifted from considering HIV to be a devastating acute condition to a chronic condition that is manageable with optimal self-management and treatment adherence. This shift in attention and disease progression requires persons living with HIV to effectively manage their health for long periods of time. However, individuals with limited health literacy may have difficulty accessing and using the health information that enables this extended health management, especially when they are presented with information that is not culturally relevant or is language inappropriate. This study will contribute evidence to support the provision of health information to diverse Latino populations in numerous ways.

This study aims to develop and evaluate an evidence-based and culturally appropriate technology (infographics embedded in a mobile application) to facilitate HIV-related communication between Latino persons living with HIV and their clinicians. By incorporating these evidence-based infographics into an app that interfaces with EHRs both locally and globally, this work will contribute to the informatics literature regarding the effective development and implementation of SMART on FHIR apps at a global scale. Additionally, it will provide valuable information regarding the effectiveness of infographics at improving clinical communication between patients and providers, which has widespread relevance to the growing information visualization literature. Additionally, there is little in the literature regarding effective ways to tailor interventions to heterogeneous groups, as an intervention designed for one Latino group may not be relevant to others. This work will provide evidence-based guidance regarding methods to effectively tailor health related interventions to diverse Latino groups. Furthermore, this intervention is scalable and will be accessible to clinicians working with Latino patients with low health literacy in the United States and around the world.

Including an additional portion in this study to ascertain if the infographics are meaningful and acceptable to non-Latino persons with HIV will provide preliminary data about the generalizability of these infographics and set the stage for further scalability of the intervention so that more individuals in need are likely to benefit from it.

F. References

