Please note, the primary outcome of interest is CD4 count, which will be collected with a review of participants' medical records following each study visit. Participants' viral load and current antiretroviral therapy regimen will also be extracted from participants' medical records following each study visit. Other measures will be in the REDCap questionnaires that will be administered using iPads.

B. Description of Populations to be Enrolled:

Individual interviews to adapt infographics to the Latino population of Denver, CO
Patient participants for interviews to identify necessary changes to infographics will be adults (≥ 18 years), Hispanic/Latino, English or Spanish-speaking, and living with HIV. If patient participants are pregnant, they may still be included.

RCT - Interventionists

Inclusion criteria for clinicians who will administer the intervention during the RCT will be those who have offered HIV-related care for greater than one year and are not planning to leave the clinic for the next year.

RCT - Patient participants

Inclusion criteria for patient participants for the RCT will be that patients are adult (≥ 18 years), Hispanic/Latino, English or Spanish-speaking, living with HIV with a detectable viral load (>30 or >40 copies/mL depending on the laboratory test) at any point in the past year or be newly diagnosed with HIV, or have an indication of adherence risk as identified by their provider and be planning to receive care at the study site for the next year. If patient participants are pregnant, they may still be included in the study. Participants from the US site are expected to reflect the demographics of Latino patients at the Center for Positive Health (CPH), who are predominantly male (85%) and Mexican (90%). Participants from the DR will reflect the population at CFLR, which is majority female (57%) and Dominican (81%).

Key-stakeholders who participate in in-depth interviews

Key-stakeholders for in-depth interviews to assess implementation factors of incorporating the SMART on FHIR app into electronic health records will be clinicians or other employees at both sites who provide HIV-related education to patients, have been working in HIV care for greater than one year, and interact with the electronic health record at their site on no less than a weekly basis.

Usability testing of Creole version of the mobile app

Table 1. Outcome measures	
Outcome	Measure
Proximal Outcomes	

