D. Description, Risks and Justification of Procedures and Data Collection Tools

Description of data collection tools

D.1. Individual interviews to adapt infographics to the Colorado context.

Participants will initially complete a brief demographic questionnaire. Then, they will complete individual interviews with a study team member. Interviews will be audio recorded and later professionally transcribed.

D.2. RCT

D.2.1. Medical record review

Data will be extracted from medical records after each study visit and will include the primary outcome CD4 count as well as most recent viral load and currently prescribed ART regimen.

D.2.2. Baseline assessments

Baseline assessment will be administered either virtually or in-person at baseline visits and will collect demographics (age, length of time living with HIV, sex, gender, income, level of education among others), assess health literacy levels with two validated assessments, the Short Assessment of Health Literacy - Spanish & English (SAHL S&E)⁶⁵ and the Newest Vital Sign (NVS),⁶⁶ include a measure of acculturation, the Short Acculturation Scale for Hispanics (SASH),⁶⁷ and all other outcome measures not extracted from medical records (Table 1).

D.2.3. Follow up assessments

Follow up assessments will be administered either virtually or in-person at 3-, 6-, and 9-month visits and will include outcome measures (Table 1) and open-ended questions exploring infographic usability, satisfaction with infographic design, and recommendations for improvement. Questions regarding interventionists' communication strategies and intervention delivery will be included to further assess intervention fidelity and enable assessment of providers' communication variability.

D.2.4. Semi-structured in-depth interviews

In depth interviews with patient participants at the CO site will be conducted using a rigorously developed iterative interview guide.⁶³ Interviews at the CO site will include questions and probes to generate an explanatory model of participants' experience living with HIV and communicating about it in a clinical setting,⁶⁸ this data was already collected from participants in the DR and NY in preliminary studies. Questions to obtain feedback on how to adapt infographics and clinical communication will be included for all participants. Interviews will be audio recorded and later transcribed.

D.2.5. Follow up interviews with interventionists

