To establish sample size for the RCT, we used a longitudinal power analysis approach for testing the “time averaged difference” in two group means for a continuous outcome over time.⁷² This effect size is analogous to Cohen’s D: $(\mu_1 - \mu_2)/\sigma$, where μ_1, μ_2 are the outcome means (averaged over time) in the treatment and control groups, and σ is the standard deviation of the outcome (assumed constant over time and equal for both groups).⁷³ Assuming a slightly less than “medium” effect size of D=0.45,⁷³ 80% power, and two-sided significance level $\alpha=0.05$, the required total sample size ranges from 68-126 depending on the assumed constant pairwise correlation between the 4 repeated measures (which we varied from 0.25 to 0.75) (Table 3). We conservatively assume a correlation of 0.75 which requires a total sample size of 126. To account for 22% attrition, higher than our attrition rate that we experienced in the pilot tests in the Dominican Republic (16%) to account for complications with this hard to reach population of Denver, we increased the sample size to 164 (161.5 rounded up to ensure equal numbers in each group).

Interviews with key stakeholders

Up to 15 interviews with key stakeholders will be conducted at each site (CO and DR). This is based on estimates that 12 interviews per site can lead to saturation of identified themes.^{74,75}

Summary of total sample size per site:

DR total # of participants to be consented to achieve study aims: 100 (maximum recruitment at this site will be 115 to account for failures and withdrawals).

Denver Health total # of participants to be consented to achieve study aims: 121 (maximum recruitment at this site will be 140 to account for failures and withdrawals).

Analytic plan for each study aim

Aim 1: See individual interviews in section C above.

Aim 2: *Conduct a multi-site randomized controlled trial to assess the efficacy of the intervention (infographics administered through a mobile app) as compared to standard care in improving treatment outcomes (CD4 count, viral load, self-efficacy to manage HIV, among others) of PWH and determine how resultant effects vary over time (baseline to 9-months) and between sites (US and CO).*

Table 3. Necessary sample size for testing the time-averaged difference between two groups of equal size				Primary	
		ρ (constant correlation of 4 repeated measures over time)			

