Effect Size (Average diff. in 2 group means over time, analogous to Cohen's D: $(\mu_1 - \mu_2)/\sigma$)		0.25	0.50	0.75	
0.20 (Small)		344	491	638	
0.35		113	161	209	
0.40		86	123	160	
0.45		68	97	126	
0.50 (Medium)		55	79	103	
0.80 (Large)		22	31	40	

Note: Calculations with 80% power and $\alpha=0.05$ with 4 repeated measures assuming exchangeable/ constant pairwise correlation " ρ " varied from 0.25 to 0.75.

Analysis: A linear mixed effect model (LMM) will be used to compare the effects of the two groups (treatment vs. standard of care) on the primary longitudinal outcome of CD4 count between baseline and the three follow up visit time points (3-, 6-, and 9-months). Subject-specific random intercepts and slopes will be used to model heterogeneity in the subjects' trajectories. Three primary tests will be considered: 1) testing the time-averaged difference in the outcome between the two treatment groups (main effect for treatment), and 2) test whether change-over-time differs between the two treatment groups (treatment*time interaction), and 3) test whether the treatment effect differs between the two sites (treatment*site interaction and treatment*site*time interaction).

Secondary Analyses: The same analysis plan will be repeated with the remaining longitudinal outcomes Table 2 of the Research Strategy section of this application. Linear mixed effect models (LMM) will be used for continuous outcomes (CD4 count, viral load, knowledge questions, engagement with health care provider scale, satisfaction with care,

self-efficacy, health related quality of life PROMIS-29), logistic generalized linear mixed effect model (GLMM) will be used for the dichotomous adherence score (SMAQ-6), and ordinal GLMM will be used for the health status assessment score while LMM will be used for the additional health status continuous score. Lastly, as a simpler alternative to longitudinal mixed effect models (that use all time points), standard general linear models will be used to model outcomes at 9 months adjusting for baseline, thus testing whether an outcome differs between the two interventions at 9 months.

The System Usability Scale (SUS) that providers complete during the second training session will be scored according to published guidelines.⁷⁶

D.9.4. Aim 3: Assess implementation factors of integrating the SMART on FHIR app into EHRs through in-depth interviews and leverage findings to ensure the app effectively interfaces with EHRs in the CO and the DR.

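### Baseline viral load is collected in a population that mixes suppressed and viraemic patients, but no CD4 analysis adjusts for it, so some precision is forgone

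*Combined protocol and SAP*

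**What the plan says.** **Eligibility.** Section IV.B (RCT - Patient participants) gives three alternative routes. The first is entry "with a detectable viral load (>30 or >40 copies/mL depending on the laboratory test) at any point in the past year". The second is new diagnosis, and the third is a provider's judgement of adherence risk. None refers to viral load on the day of enrolment.

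**Data.** Section IV.D.2.1 (Medical record review) says that, after each study visit, the record will supply "the primary outcome CD4 count as well as most recent viral load and currently prescribed ART regimen". The visits include baseline.

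**Randomisation.** Section IV.C (RCT study procedures) stratifies the permuted blocks by clinical site and by nothing else.

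**Analysis.** In section IV.F, Aim 2, the primary CD4 model is a linear mixed model with treatment, time and site terms and their interactions. On differences between patients it says: "Subject-specific random intercepts and slopes will be used to model heterogeneity in the subjects' trajectories". No baseline covariate is named. The simpler 9-month model adjusts for baseline, which reads as the baseline value of the outcome itself. Viral load appears only as a secondary outcome, and site is the only effect modifier tested.

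**The concern.** Someone detectable eleven months ago and suppressed today can sit beside someone viraemic today and beside someone just diagnosed. Their CD4 counts are likely to differ in level, and perhaps in trajectory, whichever arm they are in.

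Random intercepts and slopes describe that spread but do not remove it from a comparison between arms. A fixed effect for a baseline prognostic value would remove part of it. The time-averaged treatment difference is the test most exposed: it uses all four visits and conditions on no baseline value.

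Interpretation is also at stake. The background section says better communication can work through behaviours such as ART adherence. If so, the room for CD4 to rise may depend on viral load at entry, and the plan provides no look at this.

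**Working it through.** **Inputs from the plan (section IV.F, Table 3).** "effect size of D=0.45"; two-sided alpha 0.05; power 80%; four measures with constant correlation; "We conservatively assume a correlation of 0.75 which requires a total sample size of 126". CD4 is standardised to SD 1.

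**Step 1. Reproduce the plan.**
- Variance of the four-visit mean: V = (1 + 3 × 0.75)/4 = 0.8125.
- N = 4(1.960 + 0.842)² × 0.8125/0.45² = 125.97, so 126.
- Power = Φ(0.45/√(4 × 0.8125/126) − 1.960) = Φ(0.842) = 80.0%.
- Attrition: 126/0.78 = 161.5, raised to 164 in the plan.

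The figures stand. They use the variance without covariate adjustment.

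**Step 2. Assumptions, not in the documents.** Viraemic share at baseline p = 0.25 to 0.50. CD4 lower by d = 0.3 to 0.8 SD in viraemic patients at baseline. Correlation 0.75.

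**Step 3. Time-averaged difference, deficit persists at all visits.** Adjustment removes p(1 − p)d² from V.

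| p, d | Removed | Share of 0.8125 | Power at N = 126 |
|---|---|---|---|
| 0.25, 0.3 | 0.1875 × 0.09 = 0.0169 | 2.1% | 80.8% |
| 0.50, 0.8 | 0.25 × 0.64 = 0.1600 | 19.7% | 87.8% |

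**Step 4. Same test, 0.4 SD made up linearly by month 9.** The deficits at the four visits are d, d − 0.133, d − 0.267 and d − 0.4, so their mean is d − 0.2, or 0.1 to 0.6 SD.

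| p, d | Removed | Share of 0.8125 | Power at N = 126 |
|---|---|---|---|
| 0.25, 0.3 | 0.1875 × 0.1² = 0.0019 | 0.2% | 80.1% |
| 0.50, 0.8 | 0.25 × 0.6² = 0.0900 | 11.1% | 84.4% |

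**Step 5. 9-month model, same catch-up, baseline CD4 already in the model.** Let a = d√(p(1 − p)) and b = (d − 0.4)√(p(1 − p)). The partial R² of baseline viral load is (b − 0.75a)²/[(1 − a²)(1 − 0.75²)].
- p = 0.25, d = 0.8: a = 0.346, b = 0.173, giving 0.0075/(0.88 × 0.4375) = 1.9%.
- p = 0.50, d = 0.3: a = 0.15, b = −0.05, giving 0.0264/(0.9775 × 0.4375) = 6.2%.

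**Step 6. Estimate restricted to patients detectable at baseline.** Of 126 evaluable patients, 25-50% is 31.5 to 63. With D = 0.45 and V = 0.8125, power is 28.8% to 50.8%.

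**The case against.** **Nothing stated is wrong.** The sample size assumed no adjustment, randomisation keeps the unadjusted comparison valid, broad eligibility is a legitimate choice, and the plan is silent on covariates without excluding them. All of this stands. A reader might infer that power falls below 80%. It does not.

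**The gain may be small.** This stands in part. If the primary analysis instead compared the mean of the three follow-ups given baseline CD4, the remaining variance at correlation 0.75 would be (1 + 1.5)/3 − 0.75² = 0.2708. A viral load correlated 0.2 to 0.5 with CD4 at every visit would cut that by only 1.0% to 7.7%. But the primary model as written does not condition on baseline CD4. For the treatment-by-time test, a viral load main effect alone would add almost nothing, so the interaction with time is needed.

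**A larger 9-month figure is tempting.** Setting the raw 0.4 SD against the residual variance gives 0.1875 × 0.16/0.4375 = 6.9% to 0.25 × 0.16/0.4375 = 9.1%. That ignores what baseline CD4 already explains, so 1.9-6.2% is the relevant range.

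**Chance imbalance.** With 82 per arm and half viraemic, the 95% limit is 1.96√(0.5/82) = 15 percentage points, or about 0.08 SD at a 0.5 SD deficit. A reader might call this uncorrected bias. It is ordinary sampling error already in the standard error, and counting it beside the variance would count it twice.

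**Dilution.** A reader might infer that suppressed patients shrink the effect. If D = 0.45 held only in viraemic patients and half were suppressed, the pooled effect would be 0.225 SD and power at N = 126 about 29%. The plan does not make that assumption; it states D for the two whole arms. Nor would a covariate undo dilution. The planned viral load and adherence analyses already speak partly to this question.

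**Conclusion.** The point holds as an inexpensive improvement. The plan collects a plausible predictor of CD4 in a population whose entry routes mix its values, then leaves it out of every CD4 analysis.

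The gain in power for the time-averaged difference is from 80% to about 81-88% if the deficit persists, or about 80-84% with catch-up. In the 9-month model it is about 2-6% of residual variance beyond baseline CD4. Each range rests on the assumed 25-50% viraemic, 0.3-0.8 SD deficit and, where used, 0.4 SD catch-up. The documents supply none of these, so the true gain could be close to nil.

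The documents do not support saying that the trial is underpowered, that its primary comparison is biased, or that a null result is already explained by lack of room to improve. A subgroup estimate could inform that last question but, at 29-51% power, could not settle it.

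**What to change.** In section IV.F, Aim 2, before outcomes are compared by arm:

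1. Add baseline viral load (log10, or detectable yes/no) and its interaction with time as fixed effects in the primary CD4 mixed model.
2. Add baseline viral load as a covariate in the 9-month CD4 model, beside baseline CD4.
3. Define it as the most recent value on or before randomisation within a stated window. Section IV.D.2.1 takes the latest value in the record after the visit, which need not be a baseline value. Give one rule for results below the 30 or 40 copies/mL limits.
4. Report the treatment-by-baseline-viral-load interaction, and the estimate among participants detectable at baseline, as supportive only, with their low power stated.
5. Describe participants by entry route, including the newly diagnosed. Section IV.C itself ties the visit schedule to CD4 and viral load change after ART initiation.

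Cost: one or two degrees of freedom per model (four in the mixed model, 1 + 3, if time is fitted as four categories) and a little analysis work. Sample size, eligibility and data collection do not change.

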Permuted block randomization stratified by clinical site will be computer generated a priori and placed in ordered opaque envelopes by a study team member who is not recruiting; thus, group assignments will be blind to the study team.⁶¹ Procedures will then take place as described in Table 2.

Time intervals of study visits (baseline, 3-, 6-, and 9-months) were selected as CD4 count and viral load may change at three months after ART initiation.⁶² Study participants will have visits with interventionists (treatment group) or other providers (control group). Prior to the study, standard education at each site will be evaluated to ensure the only difference between treatment and control groups is the infographic intervention. The intervention will not be administered at 9-month visits to enable assessment of long-term effects. No extra time will be allowed for intervention study visits and participants will be reminded of visits via phone. Half of intervention visits (randomly selected) will be audio recorded and a checklist of intervention components will be independently completed by two study team members, then compared to verify intervention fidelity.

In-depth interviews with key stakeholders

Semi-structured individual interviews will be conducted with up to 15 clinicians at each site who provide patient education to establish preferences and recommendations for integrating the app into each EHR (Aim 3). Interview guides will be rigorously developed⁶³ and questions will be guided with a theoretical model.⁶⁴

Usability testing of Creole version of the mobile application

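### The primary CD4 model has no term for newly diagnosed status, a baseline factor that the protocol's own reasoning makes prognostic; the cost is precision, not validity

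*Combined protocol and SAP*

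**What the plan says.** **Eligibility (Section IV.B, RCT - Patient participants).** An adult Latino patient with HIV may enter through a detectable viral load at some point in the past year, "or be newly diagnosed with HIV, or have an indication of adherence risk as identified by their provider". The routes can overlap, and no time limit defines newly diagnosed.

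**Link to the outcome (Section IV.C, RCT study procedures).** The visit times of 0, 3, 6 and 9 months are justified on the ground that "CD4 count and viral load may change at three months after ART initiation". The same section has permuted blocks stratified by clinical site and by nothing else.

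**Data available (Section IV.D.2.2, Baseline assessments).** The baseline questionnaire records "age, length of time living with HIV, sex, gender, income, level of education", among other items.

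**Analysis (Section IV.F, Aim 2).** The primary analysis is a linear mixed model of CD4 at all four visits, with tests of the treatment main effect, treatment by time, and treatment by site (with and without time). On differing trajectories it says: "Subject-specific random intercepts and slopes will be used to model heterogeneity in the subjects" (the sentence goes on to refer to their trajectories). No baseline covariate is named. The only covariate adjustment in the plan is for the baseline value of the outcome, in a simpler 9-month model placed under secondary analyses.

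**The concern.** Newly diagnosed status is fixed before randomisation. By the protocol's own reasoning about ART initiation, it should predict how CD4 moves over the nine months. It is nevertheless neither a randomisation stratum nor a model term. A difference in CD4 course between newly diagnosed and other patients therefore stays in the unexplained between-patient variance.

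Two consequences follow, and they are the same loss seen from two sides. Averaged over possible randomisations, the standard errors are larger than they need be. In the one randomisation that occurs, an unequal share of newly diagnosed patients between arms moves the estimated effect, and the model cannot take that movement out. The treatment-by-time test is the more exposed, because the factor acts mainly on change after baseline.

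**Working it through.** **Inputs from the plan.** Section IV.F gives an "effect size of D=0.45", 80% power, two-sided alpha 0.05 and four measures with constant correlation. It then says: "We conservatively assume a correlation of 0.75 which requires a total sample size of 126". The inflation is for 22% attrition.

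**Inputs that are assumptions.** The documents do not give the share newly diagnosed (p), taken as 10% to 30%, or the extra CD4 rise after baseline in that group (d), taken as 0.5 to 1.0 SD of CD4.

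**Step 1: the plan's own figure.** The variance of a four-visit mean, in units of the CD4 variance, is (1 + 3 × 0.75)/4 = 0.8125. Then n per arm = 2 × (1.960 + 0.842)² × 0.8125/0.45² = 63, or 126 in total, which matches. For attrition, 126/0.78 = 161.5, which also matches; the plan rounds up to 164.

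**Step 2: time-averaged test.** Suppose the extra rise is present at all three follow-up visits and absent at baseline. It then shifts a patient's four-visit mean by 0.75d and adds p(1−p)(0.75d)² to the variance. Relative to 0.8125:

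| p | d | Added variance | Inflation of variance | Inflation of SE |
|---|---|---|---|---|
| 0.10 | 0.5 | 0.0127 | 1.6% | 0.8% |
| 0.20 | 0.5 | 0.0225 | 2.8% | 1.4% |
| 0.20 | 1.0 | 0.0900 | 11.1% | 5.4% |
| 0.30 | 1.0 | 0.1181 | 14.5% | 7.0% |

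This takes 0.8125 as the variance left after adjustment. If 0.8125 is instead the total before adjustment, the last row becomes 0.8125/(0.8125 − 0.1181) = 1.17. On that reading, power at 63 per arm rises with the covariate from 80.0% to 80.6% (first row) or 85.8% (last row).

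A gradual rise matters less here. If d builds up linearly to month 9, the mean shifts by only 0.5d, and the first and last rows become 0.09 × 0.0625/0.8125 = 0.7% and 0.21 × 0.25/0.8125 = 6.5%.

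**Step 3: treatment-by-time test.** With visits at 0, 1, 2 and 3 quarters, the sum of squares about the mean is 5. A patient's least-squares slope, expressed as change over nine months, has variance 9 × (1 − 0.75)/5 = 0.45. If newly diagnosed patients gain d more, linearly over nine months, the added variance is p(1−p)d².

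- p = 0.10, d = 0.5: √(1 + 0.0225/0.45) = 1.025
- p = 0.30, d = 1.0: √(1 + 0.21/0.45) = 1.211

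Other slope variation between patients dilutes this. With a further slope SD of 0.4, the base variance is 0.45 + 0.16 = 0.61 and the ratios are 1.018 and 1.159. Over slope SDs of 0 to 0.4, the standard error is 2% to 6% larger at d = 0.5 and 7% to 21% larger at d = 1.0.

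**Step 4: chance imbalance.** With 63 completers per arm, the 95% range of the between-arm difference in share is ±1.96 × √(2p(1−p)/63). That is ±10.5 percentage points at p = 0.10, ±14.0 at 0.20 and ±16.0 at 0.30. At those limits:

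- The time-averaged difference moves by 0.105 × 0.75 × 0.5 = 0.04 SD up to 0.160 × 0.75 × 1.0 = 0.12 SD, which is 9% to 27% of the 0.45 target.
- The slope difference moves by 0.38 to 1.34 of its adjusted standard error.

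About one trial in 20 would show an imbalance beyond these limits.

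**The case against.** **A much larger loss might be inferred.** One could compare the added variance with that of a baseline-adjusted mean of the three follow-up visits, (1 + 2 × 0.75)/3 − 0.75² = 0.2708. That gives an inflation of 8% (p = 0.10, d = 0.5) to 78% (p = 0.30, d = 1.0). The plan has no such estimator. Its mixed model keeps baseline among the four outcomes, and its only baseline-adjusted model concerns month 9 alone. Those figures do not describe the planned primary analysis.

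**A reader might also infer bias or a false-positive problem.** The documents do not support this. Randomisation keeps the unadjusted tests valid on average. Random intercepts and slopes put the extra heterogeneity into the standard error, which already allows for chance imbalance. The imbalance in step 4 is not a second defect.

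**The strength of the factor is not documented.** The protocol says only that CD4 may change; it gives no CD4 SD, no share newly diagnosed and no difference by diagnosis status. Nor does it describe the other patients as long treated. This stands, and it is why the size is a range that shrinks towards nothing if few patients are newly diagnosed.

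**Diagnosis is a proxy.** The protocol ties CD4 change to starting ART, and someone diagnosed years ago may be starting or restarting it. This is fair. However, the documents list the current regimen and not an ART start date for extraction, and they place extraction after each visit. Newly diagnosed status is an eligibility route, and assignment cannot alter it. A weaker proxy means a smaller gain, not a harmful adjustment.

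**Part is already covered.** The 9-month model removes whatever part of the difference follows baseline CD4. It is secondary, and baseline level does not capture a later rise that depends on starting treatment.

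**Conclusion.** The point holds as a matter of efficiency. A factor known at baseline, and prognostic on the protocol's own reasoning, is absent from both the stratification and the primary model. The sample size stands and type I error is intact on average.

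For shares of 10% to 30% and an extra rise of 0.5 to 1.0 SD, leaving the factor out makes the variance of the four-visit mean about 2% to 15% larger and the standard error of the treatment-by-time test about 2% to 21% larger. The first range assumes a rise complete by month 3; the second assumes a linear rise to month 9. Both use the plan's correlation of 0.75. The upper ends need a large share and a large difference together, and nothing in the documents shows that either is present. The change is worth making because it costs almost nothing.

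**What to change.** Before outcomes are seen by arm, add to Section IV.F:

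1. A definition of newly diagnosed at randomisation (yes/no), with a stated cut-off on length of time living with HIV. The overlapping eligibility routes do not supply one.
2. That indicator and its interaction with time as fixed effects in the CD4 and viral load mixed models. The main effect alone helps the time-averaged test; the treatment-by-time test needs the interaction.
3. A statement that baseline stays one of the repeated outcomes in these models and is not also entered as a covariate.
4. The main effect of the indicator in the 9-month baseline-adjusted models for CD4 and viral load.

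The cost is a few degrees of freedom and the need to settle a cut-off. No new data and no change to randomisation or care are required. The protocol is dated September 2023 and planned a January 2021 start. If outcomes have already been examined by arm, the adjusted model should be reported as a sensitivity analysis and labelled as added later.
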